4.5.2 Analysis of Secondary Performance Variables

Percent of patent catheters

The percent of patent catheters will be calculated by dividing the number of catheters remaining functional through completion of therapy by the total number of catheters with non-missing data on patency in the evaluable set and displayed using frequency tables. 95% confidence intervals will be additionally calculated.

Percent of placement success in single insertion attempt

The percent of placement success in a single insertion attempt will be calculated by dividing the number of catheters that are placed in a single attempt with proper tip location, and catheter patency by the total number of insertions with non-missing data on placement success and number of attempts and displayed using frequency tables. 95% confidence intervals will be additionally calculated. Data will be presented on the safety set.

Usability: Ease of insertion - based on a post-insertion survey

The usability of guidewires/stylets will be analyzed based on a composite score of performance questions administered in a post-insertion survey.

The results of the insertion user questionnaire will be tabulated. For each question, the individual results will be tabulated. Additionally, for all scores, a numerical score will be applied (5 = very easy / strongly agree; 1 = very difficult / strongly disagree) and basic statistics will be additionally presented. Data will be presented on the safety set. Cases where the use of Sherlock TLS or 3CG is documented with "No" and no documentation is available in the ease of insertion data ("empty CRF documentation") for the respective question, will be displayed as "not applicable/not used" for the corresponding question.

4.6 Other Analysis

Protocol deviation

Details regarding protocol deviations will be listed.

4.7 Missing Values

No missing value imputation methods will be applied. During the data review meeting (DRM) all participants will be reviewed regarding their occurrence of missing data on safety and performance endpoints.

4.8 Interim Analysis

All parameters captured on CRF pages belonging to data of participants needed for the interim analysis will be checked, as specified in the data validation plan and all queries will be resolved. The interim analysis will be performed at the time when 50% of the patients are enrolled. A cut-off date for the interim analysis will be fixed and all assessments done until the cut-off date will be entered in the eCRF and cleaned for the interim analysis. Only these data will be used for the interim analysis. Further unclean data entered in the eCRF will be cut and not used for the interim analysis.

As all analyses are only exploratory and no confirmatory tests are planned no alpha adjustment for the interim analysis is needed.

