## 4 STUDY DESIGN

### 4.1 Overall Design

This is a multi-center, single-arm, prospective, observational, post-market study of the PowerPICC family of devices used for both short- and long-term therapy. Only participants requiring the use of a study device as part of their standard medical care may be enrolled in the study. Study enrollment is expected to take 6 – 12 months.

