### 4.3 End of Study Definition

A participant is considered to have completed the study if he/she has completed all phases of the study including study device removal or achievement of  $180 \pm 14$ -day dwell time (last study assessment). Data collection will cease for the study participant at this point regardless of whether or not the device remains in place.

The end of the study is defined as the date of the last study assessment of the last participant in the study.

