1.2 Sample Size Considerations

The primary safety endpoint of the study is the incidence of venous thrombosis (VT). The expected venous thrombosis rate is about 10% based on literature review. The statistical rationale of the sample size is based on precision of the point estimates of the primary endpoint, as well as the ability to observe rare adverse events or complications.

Assuming the primary endpoint of VT incidence is 10% for a specific type of device, with a sample size of 150, the precision of the point estimate is 4.8% (i.e. the 95% confidence interval is the point estimate plus/minus 4.8%).

Additionally, with a sample size of 150, the probability of observing at least one rare AE/complication with a 1% rate is 78% and the probability of observing at least one rare AE/complication with a 2% rate is 95%.

A sample size of 150 is proposed for each type of device (PowerPICC, PowerPICC SOLO, and PowerGroshong PICC) for a total of 450 participants in the study.

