1.3 Interim Analysis

An interim analysis, to assess study progress, will be targeted when 50% of the subjects have completed the study, or sooner, based on reporting requirements. As all analyses are only exploratory and no confirmatory tests are planned no alpha adjustment for the interim analysis is needed.

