4.5.1 Analysis of Primary Performance Variable

The primary performance parameter for this study is the percent of PICCs that remain in place through the required therapy time period (completion of therapy) (success/failure). A success will be defined as follows:

- subjects which still have the study peripherally inserted central line catheter in place
- subjects who did not have the study peripherally inserted central line catheter in place with the reason for peripherally inserted central line catheter removal:
 - “therapy completed / end of useful medical use (catheter stayed in place through the required therapy time)” or
 - “therapy changed or cancelled”.

The percentage of PICCs that remain in place through the completion of therapy (success) will be calculated by dividing successful cases by the total number of devices with non-missing data on success/failure in the evaluable set and displayed using frequency tables. 95% confidence interval will be calculated.

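### SAP 4.8 runs the interim at 50% enrolled, against 50% completed or sooner in SAP 1.3 and Protocol 10.6; at any interim, SAP 4.5.1 also counts lines in place before day 180 as completed therapy

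*SAP*

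**What the plan says.** Three sections give the timing of the interim. SAP 4.8 is unconditional: "The interim analysis will be performed at the time when 50% of the patients are enrolled". SAP 1.3, in the same words as Protocol 10.6, says the interim "will be targeted when 50% of the subjects have completed the study, or sooner, based on reporting requirements". Under Protocol 4.3 a participant has finished on having "completed all phases of the study including study device removal or achievement of" a dwell of 180 ± 14 days, so enrolment and completion are different milestones. SAP section 5 lists one departure from the protocol, the change to non-missing denominators. It does not mention the trigger.

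SAP 4.8 uses all cleaned assessments up to a cut-off date. It does not say when that date falls relative to the trigger, or how participants still in follow-up enter the tables. Appendix A marks Tables 4.1.1 (symptomatic VT), 4.2.1.1 (complications), 5.1.1 (therapy completion) and 5.2.1 (patency) as interim outputs.

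For therapy completion, the first success category in SAP 4.5.1 is "subjects which still have the study peripherally inserted central line catheter in place", with no time condition. SAP 1.1 and Protocol 7.4 treat a line still in place as having completed therapy only once 180 days have passed.

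**The concern.** Protocol 10.6 leaves the details of the interim to the SAP, and the SAP gives two answers. Two programmers working from it could run the interim at different times and on different data, each with a section to cite.

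The success rule is a second, related problem. In the final analysis every participant who stays in follow-up has had the line removed or has reached the day-180 visit, so for them the missing time condition does little harm. At an interim, a line inserted ten days before the cut-off and recorded as in place would enter Table 5.1.1 as completed therapy. This happens under either trigger. What is at stake is how far the interim's primary performance rate, and to a less certain degree its VT rate, can be read.

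**Working it through.** **1. The plan's own figures.** SAP 1.2 assumes a VT rate of about 10% and says that "with a sample size of 150, the precision of the point estimate is 4.8" percent. Check: 1.96 × √(0.10 × 0.90 / 150) = 4.8%. The chance of at least one event is 1 − 0.99^150 = 77.9% at a 1% rate and 1 − 0.98^150 = 95.2% at a 2% rate. All three stated figures reproduce. At 225 participants the same formula gives 1.96 × √(0.09 / 225) = 3.9% overall and, with an equal split of 75 per device type (an assumption), 1.96 × √(0.09 / 75) = 6.8%.

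**2. Calendar time of the SAP 4.8 trigger.** Inputs: 450 participants (SAP 1.2, "for a total of 450 participants in the study"); enrolment period from Protocol 4.1 ("Study enrollment is expected to take 6 – 12 months"). Assumptions: uniform accrual, insertion at enrolment, cut-off on the trigger date.
- 6 months (182.5 days): the 225th participant enters at day 91. Nobody can have reached day 180, or day 166, the earliest visit in the window.
- 12 months (365 days): the 225th enters at day 182.5. At most 450 × (182.5 − 180) / 365 = 3.1 can have reached day 180, and 450 × (182.5 − 166) / 365 = 20.3 can have reached day 166.

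Almost everyone who has finished by then has finished through removal.

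**3. How many have finished.** This depends on dwell, which the documents do not give. Illustrative simulation, all inputs assumed: 0 to 75% short-term lines (3 to 29 days); long-term dwell of 30 days plus an exponential with mean 60 or 120 days, capped at 180, or all lines planned for 180 days; device-failure hazard 0.0015 per day; VT hazard 0.001 per day.

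| | 6-month accrual | 12-month accrual |
|---|---|---|
| Finished when 225 are enrolled | 15–155 (3–34% of 450) | 31–185 (7–41% of 450) |
| Ongoing among the 225 | 31–94% | 18–86% |
| Day on which 225 have finished | 121–252 | 214–339 |
| Ongoing among those enrolled that day | 25–50% | 15–46% |

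The two triggers never coincide. The completion trigger lowers the ongoing share but does not remove it.

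**4. Effect of the success rule.** Let C participants have finished with success proportion q, and let M be ongoing and recorded as in place. SAP 4.5.1 then prints (qC + M) / (C + M). Take the scenario with 50% short-term lines, long-term mean 30 + 120 days and 6-month accrual, at 225 enrolled: C = 115, q = 91.9%, M = 110. The result is (105.7 + 110) / 225 = 95.9%, against 91.0% in the final analysis of the same scenario. At 225 completed, the rate is 94.6% with ongoing lines counted as successes and 91.3% without them. Moving the trigger therefore does not cure this by itself.

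**5. VT.** In the same scenario at 225 enrolled, if every ongoing participant without VT is entered as no VT, the interim rate is 2.8% against 5.7% final. But SAP 4.4.1 divides by participants with non-missing VT data, so ongoing participants without an entry would leave the denominator. Take the scenario with every line planned for 180 days and 6-month accrual: 4.1% × 225 = 9.2 cases, 15 participants finished, final rate 14.5%. If ongoing participants without VT are missing, the denominator is at most 15 + 9.2 = 24.2, and the interim rate is at least 9.2 / 24.2 = 38%. The same data give 4.1% or 38%, on opposite sides of 14.5%, depending only on data entry.

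**The case against.** The strongest defence is that SAP 1.3 and Protocol 10.6 both allow an earlier interim, so running it at 50% enrolled is permitted. That is true of an early look when reporting requires one. It does not turn a completion milestone into a fixed enrolment milestone, and SAP 4.8 does not invoke the clause.

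The second defence is that the 180-day rule already stands in SAP 1.1 for endpoint calculations. It does, but SAP 4.5.1 is the operative definition and omits it, so the two sections need reconciling.

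Third, Table 1.2.1 (completion status) is already an interim output. That stands in part: it shows completed, withdrawn and missing, but has no row for ongoing participants and does not sit beside the endpoint rates.

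Fourth, the interim serves to assess study progress. It is exploratory, with no confirmatory test and no stopping rule. This stands in full and limits the weight of the point.

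A reader might go further and infer that most lines would be mid-dwell and that both primary interim results would lean favourably. The documents do not support this. Short-term use under 30 days is in scope and removal counts as completion, so the ongoing share could be small or large. The line-in-place item is reported with the removal data, and Protocol 1.2 schedules the removal assessment at removal or the last visit. Ongoing participants may therefore have no entry and drop out under the non-missing denominators and the no-imputation rule (SAP 4.7). A reader might also use the partly filled skin-condition block of Table 3.5, with 180 of 319 missing, as evidence of ongoing lines. The source and date of those figures are not stated, the table is not an interim output, and a missing skin result is not a line in place. Nor do the documents say that the interim is for external reporting.

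**Conclusion.** The contradiction is certain and needs no assumption: SAP 4.8 conflicts with SAP 1.3 and Protocol 10.6, and the difference is not declared. The mismatch between SAP 4.5.1 and the after-180-days rule is equally plain in the text. It affects interim Table 5.1.1 whenever ongoing lines are recorded as in place.

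That almost nobody could have reached day 180 at 50% enrolled rests on the plan's 6 to 12 months, uniform accrual and a cut-off at the trigger. The simulated ongoing shares and completion rates are illustrations under assumed dwell and hazards, not estimates for this study. The upward effect on therapy completion is conditional on ongoing lines being entered as in place; the direction for VT is undetermined. The trigger has no effect on the final analysis. The SAP should be corrected, but this does not threaten the study's conclusions.

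**What to change.** - **Trigger.** In SAP 4.8, state that the interim is run when 225 of 450 participants have completed the study (removal or day 180), or sooner if reporting requires. If the enrolment milestone is what the sponsor wants, amend SAP 1.3 and declare the change in section 5.
- **Interim Table 5.1.1.** Count a line still in place as a success only after day 180, as SAP 1.1 and Protocol 7.4 already provide, and show lines in place before day 180 in a separate ongoing row.
- **Safety tables.** Keep Tables 4.1.1 and 4.2.1.1 on the safety set, as SAP 4.4 requires, and show beside them the number still in follow-up at the cut-off. Limiting them to finished participants would discard VT already recorded in ongoing lines.

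The cost is SAP wording and one added row or footnote per table. The interim may come later, and its completion rate rests on fewer participants, with short dwells and early removals over-represented. In the extreme scenario (every line planned for 180 days, 6-month accrual, 225 enrolled) the finished-only rate is 0% against 76.4% final, so it should always be read with the ongoing count.

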4.9 Data Base Closure and Data Review

A data base closure will be performed prior to the final analysis. All parameters will be checked, as specified in the data validation plan, and all queries resolved before data base closure and final analysis.

A data snapshot will be done for the interim analysis.

A data review will be conducted prior to the interim and final analysis on all data to allocate the participants to the analysis sets. At least the following items will be discussed:

- Successful placement of a study device [listing 3.1]
- Receipt of at least one treatment through study device [listing 3.5]

These evaluations and assessments will be done together and in agreement with the Sponsor, however FGK will provide the Sponsor with the appropriate participant listings (as defined in appendix A). Data review can be done via a telephone conference or in writing.

The affiliation of participants to the analysis sets will be done prior to the analysis.

Data analysis will be done after data base closure and data review has been conducted and data review minutes have been signed by both the Sponsor and FGK.

4.10 Miscellaneous

The description of the tables in Appendix A determines the general format of the tables. The real design will be determined by the technical possibilities within SAS and may not look identical to the provided example. However, all information as displayed will be included.

For qualitative variables frequency tables (absolute and relative values) will be presented. For frequency tables, all missing values (including user-defined missing values) will be displayed in one combined category "missing", but not included in the calculation of percentages. Percentages will be presented to one decimal place. Quantitative parameters will be described by declaring the mean value, standard deviation, minimum, first quartile, median, third quartile, and maximum. In general, minimum and maximum will be presented to the same level of precision as the raw data; means and medians, and quartiles will be presented to one further decimal place; standard deviations will be printed out to one additional place further. In basic statistics tables the overall number of missing values (including user-defined missing values as "not done", "unknown", "not applicable", "not documented") will be given.

The listings are always sorted by type of device, center, and participant. If a different sorting order should be used for some listings this will be remarked separately. The variables for the special listings are explicitly given in the description of listings. All listings will be presented for the safety set and an indicator if the patient is also in the evaluable set will be added to all listings, if not stated differently.

Enrolled participants without placement of device will be considered in tables and listings describing disposition of participants, analysis sets, and inclusion and exclusion criteria. Protocol deviations will be listed for enrolled patients.

The following title will be used for all generated tables, listings, and graphs for the interim/ final analysis:

Becton Dickinson

Page # of #

Protocol: MDS-19PICCEU01 - <Interim/Final> Analysis

<Description of contents>

<Subtitle for description of contents - if applicable>

<Analysis set>

The numbering NNN of the tables/listings/graphs will be stated in the detailed description (Appendix A).

Following footnote will be used for all generated tables, listings, and graphs:

Program name: <Name of program> Date: <Actual date(DDMMYY:hhmmss)>

All tables, listings, and graphs will be generated in A4 paper format.

The statistical evaluation will be performed using SAS version 9.4 or higher.

5 Changes from Protocol

In the protocol the calculation of percentages for the safety and performance endpoints is described as dividing the numbers of participants with events by the total number of participants. This was corrected in the SAP to dividing by the number of participants with non-missing data for the respective endpoints only.

6 Signatures

This SAP will be signed electronically in the eTMF.

Statistician:
[name] Senior Statistician FGK Clinical Research GmbH [name] Germany

Sponsor:
[name] Clinical Project Manager Becton Dickinson and Company [name] Italy

Sponsor:
[name] Senior Statistician Becton Dickinson and Company [name] United States

**Statistical Analysis Plan

1.1 Disposition of Participants / Analysis Sets

- Table 1.1.1: Participants per Type of Device and Analysis Set

Enrolled Set

	Type of Device								
	PowerPICC		PowerPICC SOLO		PowerGroshong PICC		Device Not Assigned		Total
	(N=XXX)		(N=XXX)		(N=XXX)		(N=3)		(N=XXX)
Enrolled Set (ES)	N	%	N	%	N	%			N %
no									
yes									
Overall (non-missing)									

	Type of Device								
	PowerPICC		PowerPICC SOLO		PowerGroshong PICC		Device Not Assigned		Total
	(N=XXX)		(N=XXX)		(N=XXX)		(N=3)		(N=XXX)
Safety Set (SAF)	N	%	N	%	N	%			N %
no									
yes									
Overall (non-missing)									

	Type of Device								
	PowerPICC		PowerPICC SOLO		PowerGroshong PICC		Device Not Assigned		Total
	(N=XXX)		(N=XXX)		(N=XXX)		(N=3)		(N=XXX)
Evaluable Set (EVS)	N	%	N	%	N	%			N %
no									
yes									
Overall (non-missing)									

Footnote 1: For the subsequent tables, listings, and graphs, only the short labels for the statistical analysis sets (given in brackets) are used.

- Table 1.1.2: Participants per Analysis Set and Center

Enrolled Set

Center	Analysis Set					
	Enrolled Set (N=XXX)		Evaluable Set (N=XXX)		Safety Set (N=XXX)	
	N	%	N	%	N	%
1						
2						
3						
4						
...						
Overall (non-missing)						

- Table 1.1.3: Participants per Analysis Set and Device

Enrolled Set

Device	Analysis Set					
	Enrolled Set (N=XXX)		Evaluable Set (N=XXX)		Safety Set (N=XXX)	
	N	%	N	%	N	%
missing						
PowerPICC						
PowerPICC SOLO						
PowerGroshong PICC						
Device Not Assigned						
Overall (non-missing)						

- Table 1.1.4: Participants per Analysis Set and Country

Enrolled Set

Country	Analysis Set					
	Enrolled Set (N=XXX)		Evaluable Set (N=XXX)		Safety Set (N=XXX)	
	N	%	N	%	N	%
...						
...						
...						
Overall (non-missing)						

- Table 1.1.5: Inclusion and Exclusion Criteria

Enrolled Set

	Type of Device									
	PowerPICC		PowerPICC SOLO		PowerGroshong PICC		Device Not Assigned		Total	
	(N=xxx)		(N=xxx)		(N=xxx)		(N=3)		(N=xxx)	
All inclusion criteria met	N	%	N	%	N	%			N	%
no										
yes										
Overall (non-missing)										

	Type of Device									
	PowerPICC		PowerPICC SOLO		PowerGroshong PICC		Device Not Assigned		Total	
	(N=xxx)		(N=xxx)		(N=xxx)		(N=3)		(N=xxx)	
None of the exclusion criteria met	N	%	N	%	N	%			N	%
no										
yes										
Overall (non-missing)										

	Type of Device									
	PowerPICC		PowerPICC SOLO		PowerGroshong PICC		Device Not Assigned		Total	
	(N=xxx)		(N=xxx)		(N=xxx)		(N=3)		(N=xxx)	
All inclusion criteria and none of the exclusion criteria met	N	%	N	%	N	%			N	%
no										
yes										
Overall (non-missing)										

- Listing 1.1.1: Disposition of Participants and Analysis Sets

Enrolled Set

Variables: Type of device, Center, Country, Participant, ICF version date, Date/Time ICF signed, All IC and EC met (yes/no), Violated IC^, Violated EC^, Agreed to use the study data for further research, Subject status, EVS (yes/no), SAF (yes/no)

Footnote 1: ^ Numbers (eCRF) of violated IC or EC.

Note: Type of device will be displayed as “by-variable” within a subtitle.

1.2 Discontinuation

- Table 1.2.1: Status at End of Study (*)

Safety Set

	Type of Device							
	PowerPICC (N=xxx)		PowerPICC SOLO (N=xxx)		PowerGroshong PICC (N=xxx)		Total (N=xxx)	
Completion status (CRF)	N	%	N	%	N	%	N	%
missing								
completed (removal and/or 180 days)								
withdrawal								
Overall (non-missing)								

	Type of Device							
	PowerPICC (N=xxx)		PowerPICC SOLO (N=xxx)		PowerGroshong PICC (N=xxx)		Total (N=xxx)	
Reason for withdrawal	N	%	N	%	N	%	N	%
missing								
withdrawal of consent								
lost to follow up								
death								
AE								
device deficiency								
other								
Overall (non-missing)								

Note 1: Reason for withdrawal only displayed for patients with study withdrawal.

	Type of Device							
	PowerPICC (N=xxx)		PowerPICC SOLO (N=xxx)		PowerGroshong PICC (N=xxx)		Total (N=xxx)	
Completion status	N	%	N	%	N	%	N	%
missing								
completed (removal and/or 180 days)								
death								
lost to follow up								
withdrawal								
Overall (non-missing)								

- Listing 1.2.1: Study Termination

Safety Set

Variables: Type of device, Participant, Date of study completion, Completion status, Reason for withdrawal, Specification of other reason, Date of death, EVS (yes/no), SAF (yes/no)

Note: Type of devices will be displayed as “by-variable” within a subtitle.

2 Demographic Data and Other Covariates

- Table 2.1: Participant Demographics – Frequencies

Safety Set

	Type of Device							
	PowerPICC (N=xxx)		PowerPICC SOLO (N=xxx)		PowerGroshong PICC (N=xxx)		Total (N=xxx)	
Gender	N	%	N	%	N	%	N	%
missing								
male								
female								
Overall (non-missing)								

	Type of Device							
	PowerPICC (N=xxx)		PowerPICC SOLO (N=xxx)		PowerGroshong PICC (N=xxx)		Total (N=xxx)	
Race	N	%	N	%	N	%	N	%
missing								
White								
Asian								
Black or African American								
other								
unknown								
Overall (non-missing)								

- Table 2.2: Participant Demographics – Basic Statistics

Safety Set

		Type of Device			Total (N=xxx)
		PowerPICC (N=xxx)	PowerPICC SOLO (N=xxx)	PowerGroshong PICC (N=xxx)	
Age [years] [^]	N				
	missing				
	mean				
	SD				
	minimum				
	1st quartile				
	median				
	3rd quartile				
	maximum				

Footnote 1: [^] Age at signing informed consent.

		Type of Device			Total (N=xxx)
		PowerPICC (N=xxx)	PowerPICC SOLO (N=xxx)	PowerGroshong PICC (N=xxx)	
Body height [cm]	N				
	missing				
	mean				
	SD				
	minimum				
	1st quartile				
	median				
	3rd quartile				
	maximum				

Body weight [kg]	N				
	missing				
	mean				
	SD				
	minimum				
	1st quartile				
	median				
	3rd quartile				
	maximum				

BMI [kg/m²]	N				
	missing				
	mean				
	SD				
	minimum				
	1st quartile				
	median				
	3rd quartile				
	maximum				

- Listing 2.1: Participant Demographics

Safety Set

Variables: Type of device, Participant, Age [years][^], Gender, Race (including specification of other race), Body height [cm], Body weight [kg], BMI [kg/m²], Evaluable Set (yes/no)

Footnote 1: [^] Age at signing informed consent.

Note: Type of devices will be displayed as “by-variable” within a subtitle.

- Table 2.3: Medical History

Safety Set

	Type of Device							
	PowerPICC (N=xxx)		PowerPICC SOLO (N=xxx)		PowerGroshong PICC (N=xxx)		Total (N=xxx)	
Implantable devices	N	%	N	%	N	%	N	%
missing								
no								
yes								
Overall (non-missing)								

	Type of Device							
	PowerPICC (N=xxx)		PowerPICC SOLO (N=xxx)		PowerGroshong PICC (N=xxx)		Total (N=xxx)	
Past and/or current use of an artificial heart	N	%	N	%	N	%	N	%
missing								
no								
yes								
Overall (non-missing)								

	Type of Device							
	PowerPICC (N=xxx)		PowerPICC SOLO (N=xxx)		PowerGroshong PICC (N=xxx)		Total (N=xxx)	
Past and/or current anatomical abnormalities of the central venous system	N	%	N	%	N	%	N	%
missing								
no								
yes								
Overall (non-missing)								

	Type of Device							
	PowerPICC (N=xxx)		PowerPICC SOLO (N=xxx)		PowerGroshong PICC (N=xxx)		Total (N=xxx)	
Past and/or current use of an atrial fibrillation or other atrial arrhythmias that affects the p-wave	N	%	N	%	N	%	N	%
missing								
no								
yes								
Overall (non-missing)								

	Type of Device							
	PowerPICC (N=xxx)		PowerPICC SOLO (N=xxx)		PowerGroshong PICC (N=xxx)		Total (N=xxx)	
Known absence of a p-wave	N	%	N	%	N	%	N	%
missing								
no								
yes								
Overall (non-missing)								

	Type of Device							
	PowerPICC (N=xxx)		PowerPICC SOLO (N=xxx)		PowerGroshong PICC (N=xxx)		Total (N=xxx)	
Abnormalities of the arms	N	%	N	%	N	%	N	%
missing								
no								
yes								
Overall (non-missing)								

	Type of Device							
	PowerPICC (N=xxx)		PowerPICC SOLO (N=xxx)		PowerGroshong PICC (N=xxx)		Total (N=xxx)	
Abnormalities of the chest wall	N	%	N	%	N	%	N	%
missing								
no								
yes								
Overall (non-missing)								

	Type of Device							
	PowerPICC (N=xxx)		PowerPICC SOLO (N=xxx)		PowerGroshong PICC (N=xxx)		Total (N=xxx)	
History of coagulopathy	N	%	N	%	N	%	N	%
missing								
no								
yes								
Overall (non-missing)								

	Type of Device							
	PowerPICC (N=xxx)		PowerPICC SOLO (N=xxx)		PowerGroshong PICC (N=xxx)		Total (N=xxx)	
History of hypercoagulopathy	N	%	N	%	N	%	N	%
missing								
no								
yes								
Overall (non-missing)								

	Type of Device							
	PowerPICC (N=xxx)		PowerPICC SOLO (N=xxx)		PowerGroshong PICC (N=xxx)		Total (N=xxx)	
Current treatment with anticoagulants	N	%	N	%	N	%	N	%
missing								
no								
yes								
Overall (non-missing)								

	Type of Device							
	PowerPICC (N=xxx)		PowerPICC SOLO (N=xxx)		PowerGroshong PICC (N=xxx)		Total (N=xxx)	
Central venous access devices	N	%	N	%	N	%	N	%
missing								
no								
yes								
Overall (non-missing)								

	Type of Device							
	PowerPICC (N=xxx)		PowerPICC SOLO (N=xxx)		PowerGroshong PICC (N=xxx)		Total (N=xxx)	
History of lymph node dissection/lymphedema	N	%	N	%	N	%	N	%
missing								
no								
yes								
Overall (non-missing)								

	Type of Device							
	PowerPICC (N=xxx)		PowerPICC SOLO (N=xxx)		PowerGroshong PICC (N=xxx)		Total (N=xxx)	
Renal impairment	N	%	N	%	N	%	N	%
missing								
no								
yes								
Overall (non-missing)								

	Type of Device							
	PowerPICC (N=xxx)		PowerPICC SOLO (N=xxx)		PowerGroshong PICC (N=xxx)		Total (N=xxx)	
Treated with cervical collars or halo traction	N	%	N	%	N	%	N	%
missing								
no								
yes								
Overall (non-missing)								

	Type of Device							
	PowerPICC (N=xxx)		PowerPICC SOLO (N=xxx)		PowerGroshong PICC (N=xxx)		Total (N=xxx)	
History of phlebitis	N	%	N	%	N	%	N	%
missing								
no								
yes								
Overall (non-missing)								

	Type of Device							
	PowerPICC (N=xxx)		PowerPICC SOLO (N=xxx)		PowerGroshong PICC (N=xxx)		Total (N=xxx)	
History of venous thrombosis	N	%	N	%	N	%	N	%
missing								
no								
yes								
Overall (non-missing)								

	Type of Device							
	PowerPICC (N=xxx)		PowerPICC SOLO (N=xxx)		PowerGroshong PICC (N=xxx)		Total (N=xxx)	
History of deep vein thrombosis	N	%	N	%	N	%	N	%
missing								
no								
yes								
Overall (non-missing)								

	Type of Device							
	PowerPICC (N=xxx)		PowerPICC SOLO (N=xxx)		PowerGroshong PICC (N=xxx)		Total (N=xxx)	
History of catheter related bloodstream infection	N	%	N	%	N	%	N	%
missing								
no								
yes								
Overall (non-missing)								

	Type of Device							
	PowerPICC (N=xxx)		PowerPICC SOLO (N=xxx)		PowerGroshong PICC (N=xxx)		Total (N=xxx)	
Other relevant Medical History	N	%	N	%	N	%	N	%
missing								
no								
yes								
Overall (non-missing)								

- Listing 2.2: Medical History

Safety Set

Variables: Type of device, Participant + all variables on medical history-form, Evaluable Set (yes/no)

Note: Type of devices will be displayed as “by-variable” within a subtitle.

- Listing 2.3: Other Medical History

Safety Set

Variables: Type of device, Participant, Sequence No., Term/Description, Start date, End date, Status (ongoing), Evaluable Set (yes/no)

Footnote 1: Only participants with at least one entry in 'Other Medical History' form are displayed.

- Table 2.4: Baseline Information

Safety Set

	Type of Device							
	PowerPICC (N=xxx)		PowerPICC SOLO (N=xxx)		PowerGroshong PICC (N=xxx)		Total (N=xxx)	
	N	%	N	%	N	%	N	%
Primary diagnosis for current admission								
missing								
cardiac								
orthopedic								
...								
Overall (non-missing)								

	Type of Device							
	PowerPICC (N=xxx)		PowerPICC SOLO (N=xxx)		PowerGroshong PICC (N=xxx)		Total (N=xxx)	
	N	%	N	%	N	%	N	%
Secondary diagnosis for current admission								
missing								
cardiac								
orthopedic								
...								
Overall (non-missing)								

	Type of Device											
	PowerPICC			PowerPICC SOLO			PowerGroshong PICC			Total		
	(N=xxx)		(N=xxx)		(N=xxx)		(N=xxx)		(N=xxx)		(N=xxx)	
	Number of Reasons	Number of Part. with Reason	Part. with Reason	Number of Reasons	Number of Part. with Reason	Part. with Reason	Number of Reasons	Number of Part. with Reason	Part. with Reason	Number of Reasons	Number of Part. with Reason	Part. with Reason
	(N#)	(N)	(%)	(N#)	(N)	(%)	(N#)	(N)	(%)	(N#)	(N)	(%)
Reason for PICC placement												
limited peripheral access												
IV therapy/pain management												
...												
Total												

	Type of Device							
	PowerPICC		PowerPICC SOLO		PowerGroshong PICC		Total	
	N	%	N	%	N	%	N	%
Intended access duration								
missing								
short-term (<30 days)								
long-term (>= 30 days)								
Overall (non-missing)								

- Listing 2.4: Baseline Information

Safety Set

Variables: Type of device, Participant, Primary diagnosis for current admission / Specification of other, Secondary diagnosis for current admission / Specification of other, Reason for PICC placement / Specification of other reason, Intended access duration, Evaluable Set (yes/no)

Note: Type of devices will be displayed as “by-variable” within a subtitle.

3 Catheter Insertion, Maintenance and Removal

- Table 3.1: Catheter Insertion: Procedure Details

Safety Set

	Type of Device							
	PowerPICC (N=xxx)		PowerPICC SOLO (N=xxx)		PowerGroshong PICC (N=xxx)		Total (N=xxx)	
	N	%	N	%	N	%	N	%
Location of procedure performance								
missing								
bedside								
interventional radiology								
other								
Overall (non-missing)								

	Type of Device							
	PowerPICC (N=xxx)		PowerPICC SOLO (N=xxx)		PowerGroshong PICC (N=xxx)		Total (N=xxx)	
	N	%	N	%	N	%	N	%
Catheter tip repositioning								
missing								
no								
yes								
Overall (non-missing)								

	Type of Device							
	PowerPICC (N=xxx)		PowerPICC SOLO (N=xxx)		PowerGroshong PICC (N=xxx)		Total (N=xxx)	
	N	%	N	%	N	%	N	%
Device placement successful								
missing								
no								
yes								
Overall (non-missing)								

- Table 3.2: Catheter Insertion: Duration

Safety Set

		Type of Device			Total (N=xxx)
		PowerPICC (N=xxx)	PowerPICC SOLO (N=xxx)	PowerGroshong PICC (N=xxx)	
Duration between start and PICC is secured [min]	N				
	missing				
	mean				
	SD				
	minimum				
	1st quartile				
	median				
	3rd quartile				
	maximum				

		Type of Device			Total (N=xxx)
		PowerPICC (N=xxx)	PowerPICC SOLO (N=xxx)	PowerGroshong PICC (N=xxx)	
Duration between start and tip position confirmation [min]	N				
	missing				
	mean				
	SD				
	minimum				
	1st quartile				
	median				
	3rd quartile				
	maximum				

- Listing 3.1: Catheter Insertion: Procedure Details

Safety Set

Variables: Type of device, Participant, Where was the procedure performed / Specification, Insertion date, Procedure start time/stop time, Time of tip location confirmation, Duration between start and PICC is secured [min], Duration between start and tip position confirmation [min], Catheter tip repositioned, Device placement successful, Evaluable Set (yes/no)

Note: Type of devices will be displayed as “by-variable” within a subtitle.

- Table 3.3: Catheter Insertion: Device

Safety Set

Device	Type of Device							
	PowerPICC (N=xxx)		PowerPICC SOLO (N=xxx)		PowerGroshong PICC (N=xxx)		Total (N=xxx)	
	N	%	N	%	N	%	N	%
missing								
PowerGroshong PICC-Single - 5F- 40 cm								
PowerGroshong PICC-Single - 5F- 45 cm								
...								
Overall (non-missing)								

Guidewire	Type of Device							
	PowerPICC (N=xxx)		PowerPICC SOLO (N=xxx)		PowerGroshong PICC (N=xxx)		Total (N=xxx)	
	N	%	N	%	N	%	N	%
missing								
BD nitinol 70 cm								
BD nitinol 135 cm								
...								
Overall (non-missing)								

	Type of Device							
	PowerPICC (N=xxx)		PowerPICC SOLO (N=xxx)		PowerGroshong PICC (N=xxx)		Total (N=xxx)	
Placement of catheter	N	%	N	%	N	%	N	%
missing								
right arm								
left arm								
other								
Overall (non-missing)								

	Type of Device							
	PowerPICC (N=xxx)		PowerPICC SOLO (N=xxx)		PowerGroshong PICC (N=xxx)		Total (N=xxx)	
Vein	N	%	N	%	N	%	N	%
missing								
basilic								
cephalic								
...								
Overall (non-missing)								

	Type of Device							
	PowerPICC (N=xxx)		PowerPICC SOLO (N=xxx)		PowerGroshong PICC (N=xxx)		Total (N=xxx)	
Vessel/catheter ratio done prior to insertion	N	%	N	%	N	%	N	%
missing								
no								
yes								
Overall (non-missing)								

	Type of Device							
	PowerPICC (N=xxx)		PowerPICC SOLO (N=xxx)		PowerGroshong PICC (N=xxx)		Total (N=xxx)	
Number of insertion attempts	N	%	N	%	N	%	N	%
missing								
1								
2								
..								
Overall (non-missing)								

	Type of Device							
	PowerPICC (N=xxx)		PowerPICC SOLO (N=xxx)		PowerGroshong PICC (N=xxx)		Total (N=xxx)	
Local anaesthesia used	N	%	N	%	N	%	N	%
missing								
no								
yes								
Overall (non-missing)								

- Listing 3.2: Catheter Insertion: Device

Safety Set

Variables: Type of device, Participant, What device was placed, What guidewire was used / Specification, Kit / tray catalog number, Kit / tray lot number, Kit / tray expiration date, More than 1 kit used, Where was catheter placed / Specification, Which vein was accessed / Specification, Assessment of the vessel/catheter ratio done, Vessel diameter, Vessel to catheter ratio, No. of insertion attempts, Local anaesthesia used, Evaluable Set (yes/no)

Note: Type of devices will be displayed as “by-variable” within a subtitle.

- Listing 3.3: Catheter Insertion: Additional Kits

Safety Set

Variables: Type of device, Participant, Sequence No., Kit / tray catalog number, Kit / tray lot number, Kit / tray expiration date, Implanted catheter from this kit, Guidewire used from this kit, Evaluable Set (yes/no)

Note: Type of devices will be displayed as “by-variable” within a subtitle.

- Table 3.4: Catheter Insertion: Insertion

Safety Set

	Type of Device							
	PowerPICC (N=xxx)		PowerPICC SOLO (N=xxx)		PowerGroshong PICC (N=xxx)		Total (N=xxx)	
	N	%	N	%	N	%	N	%
Catheter length trimmed								
missing								
no								
yes								
